### **Analytical Plan**

**Primary Outcome** – Mean Within-Subject Difference in daily sleep duration during 3 treatment periods from baseline. Participant's sleep duration will be measured objectively using Fitbit devices and by self-reported questionnaires. The Fitbit devices will collect information continuously that will be stored in Fitabase, a secure, online portal. Participant sleep activity will be aggregated by day.

Analysis of Primary Outcome: The effect of the personalized MBI intervention on individual's sleep duration will be assessed in each arm separately. Individual changes in the average daily sleep durations between the run-in and each treatment period will be reported using mean (95% confidence intervals CIs). Bland-Altman plots will be constructed to visualize the agreement between the Fitbit reported and self-reported sleep duration. The effects of treatment on sleep duration will be assessed using generalized estimating equations (GEE) with an unstructured variance-covariance matrix for measures on the same day to that night's sleep. This model accounts for possible autocorrelation and linear trends between sleep duration across time. The GEE models will include time of day of treatment exposure (AM versus PM) as a covariate.

**Exploratory Aim 1 Outcomes** - Mean Within-Subject Difference in daily sleep quality and other physiological factors during 3 treatment periods from baseline. This aim will explore the effects of the personalized intervention on sleep quality components (sleep onset, sleep staging, and overall sleep score) and physiological factors (breathing/resting heart rate, heart rate variability (HRV) and physical activity). All these measurements will be recorded and aggregated daily by the Fitbit device.

Analysis of Exploratory Aim 1 Outcome: The effect of the personalized MBI intervention on individual's sleep quality and physiological factors will be assessed in each arm separately. Individual changes in the average daily sleep quality (e.g., score), heart rate and daily average number of steps between the run-in and each treatment period will be reported using means (95% CIs. GEE models will be employed to test the effect of the intervention of sleep quality and physiological factors.

**Exploratory Aim 2 Outcomes** – Mean Within-Subject Difference in perceived stress, anxiety and depression scores measured objectively during 3 treatment

periods from baseline. Participants' perceived stress score will be measured using the EMA questionnaire and PSS; anxiety and depressive disorder scores will be assessed using the PHQ-4 questionnaire. EMA, PSS and PHQ-4 will be evaluated pre-intervention (run-in), bi-weekly during the intervention, and post-intervention. Analysis of Exploratory Aim 2 Outcomes: To explore the role of anxiety and depression as a potential mediator(M) between perceived stress (X) and sleep quality (Y) we will employ three mixed effects regression models (Fig 2).

[figure not shown]

Figure 2 Mediation Model

We will estimate the (c'), the indirect effect (ab), and the total effect of perceived stress quality ( $c = ab + c'$ ).

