### **Rationale for Selecting Sleep Duration as a Personalized Trial**

Sleep is an important and complex physiological process for maintaining optimal health. The National Sleep Foundation recommends  $\geq 7$ h of sleep per night on a regular basis for adults aged 18-60 years. During the first two COVID-19 pandemic waves, findings indicated a high prevalence of both poor sleep quality and moderate-severe stress in healthcare workers (HCWs) (either at the frontline or not), and especially amongst women. Studies conducted in a cohort of New York City HCWs (80% women,  $>50\%$  nurses, median age of 36 years) showed that during the pandemic, the rates of insomnia symptoms (e.g., short duration, poor quality sleep) were approximately 20% higher than rates reported in 2018, and revealed an association between poor sleep quality and a higher prevalence of psychological distress. Thus, evidence suggests that sleep may be a target intervention to decrease psychological distress among HCWs. While some mitigation interventions (e.g., reducing workload) have been proposed to address stress/burnout on HCWs very few have focused on women in healthcare and specifically targeted sleep as a symptom of stress. The primary goal of this pilot study is to determine if a personalized trial (N-of-1) employing a Mind-Body Intervention (MBI) can produce a meaningful increase in sleep duration among women 40-60 years of age and older working at Northwell Health. N-of-1 studies are single-patient crossover trials, where individual patients are given candidate treatments in a random sequence of alternating periods to determine the most effective treatment for that patient. In contrast to randomized controlled trials, which provide evidence on a population level, N-of-1 trials provide a method to determine what works best for the individual directly. Up to 65 women with a history of short sleep duration (defined as an average  $<7$ h per 24-h period for at least three months) will be enrolled (randomized) over a period of two years. Participants will complete a 2-week run-in period with no intervention, for baseline data collection, including bi-weekly surveys and Fitbit-derived sleep and activity data. Those who are deemed eligible and achieve at least 80% adherence of Fitbit wear and survey submission will be randomized to Arm 1 (N=30) or Arm 2 (N=30). Each arm will receive a personalized intervention comprised of three components: mindfulness, yoga and guided walking assigned in 2-week block sequences for a total period of 12 weeks. Following the intervention, all participants will be assessed over a 2-week follow-up period. Changes in average daily sleep duration will be calculated for each participant based on daily measurements between the run-in and each treatment period. The Fitbit devices will also record sleep quality components (sleep onset, sleep staging, and overall sleep score) and physiological factors (resting heart rate, heart rate variability (HRV) and activity). **We will also examine the direct and indirect relationships between perceived stress, anxiety and depression, and sleep quality assessed pre, during (bi-weekly), and post MBI.**

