
Participant report of poor sleep duration meets all of our criteria for selection as a use case as outlined in our umbrella grant: it has high public health burden; high heterogeneity of therapy response; multiple, evidenced-based treatments; and is high priority for a Personalized Trial approach as determined by previously interviewed clinicians and patients. A recent study of US workers found the prevalence of short sleep duration to be 37.6% and poor sleep quality to be 19.2%,

supporting the need for innovative treatments. This instance will adapt our N-of-1 trial platform to be able to deliver a three component Mind-Body Intervention with the goal of meaningfully increasing average daily sleep duration as compared with the baseline period.

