## 7. ELIGIBILITY CRITERIA

- *Describe the characteristics of the subject population, including their anticipated number, age, ranges, sex, ethnic background, and health status. Identify the criteria for inclusion or exclusion of any subpopulation.*
- *Explain the rationale for the involvement of special classes of subjects, such as fetuses, pregnant women, children, prisoners or other institutionalized individuals, or others who are likely to be vulnerable. You cannot include these populations in your research, unless you indicate such in the protocol*

- *Similarly, detail exclusionary criteria: age limits, special populations (minors, pregnant women, decisionally impaired), use of concomitant medications, subjects with other diseases, severity of illness, etc.*

Up to 65 participants will be randomized to receive this pilot study protocol. We aim to recruit a diverse pool of participants with varied ethnic and racial backgrounds.

Inclusion:

- Age 40 – 60 years
- Sex assigned at birth-female
- Northwell employee or affiliate
- Self-reported history of short sleep duration (<7h per 24-h period) for at least 3 months
  - After a 2-week run-in, Fitbit verified short sleep duration, and ≥80% adherence of Fitbit wear and survey submission
- Self-report of perceived stress ≥18 using the Perceived Stress Scale (PSS)
- Owns and can regularly access a smartphone capable of receiving text messages
- Owns and can regularly access an e-mail account
- Willingness to wear a Fitbit device

Exclusion:

- Age < 40 or > 60 years old
- Sex assigned at birth- male
- Not a Northwell employee
- No history of short sleep duration or non-adherent to the Fitbit wear and survey submission
- Self report of perceived stress <18 using the Perceived Stress Scale (PSS)
- Women who are pregnant or breastfeeding
- Does not own or cannot regularly access a smartphone capable of receiving text messages
- Does not possess or cannot regularly access an email account
- Deemed unable to complete the study protocol as a result of cognitive impairment, severe medical or mental illness, or active or prior substance abuse
- Planned surgeries within 6 months from study start date
- Participants who have been previously told by a clinician they have mobility limiting health conditions and/or not to engage in walking for 30 minutes, three times per week or yoga

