## 8. NUMBER OF SUBJECTS

- *Indicate the total number of subjects to be accrued locally. If applicable, distinguish between the number of subjects who are expected to be pre-screened, enrolled (consent obtained), randomized and complete the research procedures.*
- *If your study includes different cohorts, include the total number of subjects in each cohort.*
- *If this is multisite study, include total number of subjects across all sites.*

Up to 1000 potential participants may be screened for study eligibility. Up to 65 participants will be randomized until 60 (30 participants in each arm) complete research procedures with any data (Fitbit or survey) post- randomization. Eligible participants will be randomized (1:1) into Arm 1 or Arm 2. In Arm 1 (N=30), participants will receive a personalized intervention comprised of three components delivered in a ABCCBA sequence over a total period of 12 weeks, where A- mindfulness, B-yoga, and C-guided walking. During each 2-weeks block, participants will be prompted to complete 3 x 30-minute intervention sessions weekly. In Arm 2 (N=30), participants will receive a personalized intervention comprised of the same three components delivered in a CBAABC sequence over a total period of 12 weeks. Prompts will be delivered weekly to Arm 2 as well.

[figure not shown]

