## 16. WITHDRAWAL OF SUBJECTS

- *Describe anticipated circumstances under which subjects will be withdrawn from the research without their consent*
- *Describe procedures for orderly termination*
- *Describe procedures that will be followed when subjects withdraw from the research, including partial withdrawal from procedures with continued data collection.*

Circumstances under which participants will be withdrawn from the research without their consent include not meeting objective verification of short sleep duration (<7 hrs per 24hr periods during 2 week run-in as measured by a Fitbit activity tracker), failure to maintain protocol adherence, and self-reported adverse side effects to interventions. A potential participant will not be randomized to receive the intervention protocol until he/she has demonstrated at least 80% adherence to continuous Fitbit monitoring (activity recorded > 12 hours/day, and

recorded sleep activity >180 minutes) and response to survey questionnaires during the baseline period.

Potential participants will be notified of the possibility of being removed from the study before intervention randomization due to adherence issues in the informed consent. Participants who fail to maintain minimum adherence during baseline will be notified by the research team in the first 10-14 days of baseline participation. These participants will stop receiving notifications and survey prompts and will receive instructions to un-link their Fitbit device.

Participants who fail to maintain protocol during the intervention period will be contacted by a member of the study team with a reminder of the study protocol and will be informed that this may impact their continued study eligibility. If it is determined that the participant will be withdrawn from the study, the participant will be notified of their withdrawal from the study by the research team. The participant will stop receiving notifications and survey prompts and will be sent instructions to un-link their Fitbit device. The participant will be able to keep their Fitbit device.

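### The run-in nights that must show sleep under 7 h are also the baseline for the primary change, so the within-arm gain includes upward regression to the mean that the planned GEE does not remove

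*Combined protocol and SAP*

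**What the plan says.** **Outcome and baseline.** Section 12 (Analytical Plan) defines the primary outcome as "Mean Within-Subject Difference in daily sleep duration during 3 treatment periods from baseline". Section 3 says how it is formed: "Changes in average daily sleep duration will be calculated for each participant based on daily measurements between the run-in and each treatment period". Section 9 treats the run-in as the period in which baseline sleep is measured. Section 3 also states the aim, "with the goal of meaningfully increasing average daily sleep duration as compared with the baseline period".

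**Entry check on the same nights.** Section 7 requires "Fitbit verified short sleep duration" after the 2-week run-in. Section 16 withdraws people for "not meeting objective verification of short sleep duration (<7 hrs per 24hr periods during 2 week run-in as measured by a Fitbit activity tracker". Section 3 points to an average, "Up to 65 women with a history of short sleep duration (defined as an average" below 7 h, but neither section 7 nor section 16 says that the run-in check uses the run-in average.

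**A second description of entry.** Section 11 (Research Procedures) and the randomisation paragraph of section 12 make 80% adherence the condition for randomisation and do not mention the 7 h check. Adherence has its own sleep threshold, given in section 16 as "recorded sleep activity >180 minutes". Sections 3 and 9 require people to be both eligible and adherent.

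**Comparison and model.** Effects are assessed within each arm. Arm 1 receives ABCCBA. In Arm 2, "participants will receive a personalized intervention comprised of the same three components delivered in a CBAABC sequence". The GEE is said to allow for autocorrelation and a linear trend, and its one named covariate is AM or PM exposure. Regression to the mean is not mentioned.

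**The concern.** A run-in average is a person's usual sleep plus two weeks of chance variation. A cut at 7 h keeps people whose chance variation happened to be low more readily than people whose variation was high. Later nights do not carry that selection, so average sleep rises after the run-in even if the intervention does nothing.

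The planned change subtracts exactly the selected nights. Randomisation cannot help, because it only orders the three components and leaves no untreated group. The affected quantity is the primary estimate: an arm with no benefit would show a significant gain more often than intended. Contrasts between components are much less exposed when nights are weakly correlated.

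**Working it through.** **Inputs from the documents.** Run-in 14 nights, treatment 84 nights, follow-up 14 nights; 30 per arm; entry cut 7 h; adherence floor 180 min on 80% of nights; within-subject SD at most 2 h; AR(1) 0.95.

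**Assumptions.** Mean sleep of those entering the run-in (6.0, 6.5 or 7.0 h), between-person SD, and smaller SDs and correlations than the plan's. The 7 h check is read as the run-in average. The 180-minute rule is applied as at least 12 of 14 nights over 3 h (80% of 14 is 11.2), with recorded sleep taken as true sleep.

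**The plan's own figure.** The plan gives no size for this bias, so there is none to reproduce. The SD and correlation come from its sample-size paragraph. Its 30 per arm at 80% power did not reproduce: two independent means at 0.7 SD need 33 per arm, and 28-night means at AR(1) 0.95 need 21. That is a separate point and does not affect this one.

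**Closed form, weak correlation (7 h cut only).** Shift = (V/S) × φ(c)/Φ(c). V is the chance variance of the 14-night mean, S the SD of the run-in mean, and c = (7 − mean)/S. Take mean 6.5 h, between-person SD 0.8 h, nightly SD 1.5 h, correlation 0.3.
- f(14) = [1 + 2Σ(1 − k/14)0.3^k]/14 = 0.1264, so V = 1.5² × 0.1264 = 0.284.
- S = √(0.64 + 0.284) = 0.961; c = 0.5/0.961 = 0.520; φ/Φ = 0.3485/0.6985 = 0.499.
- Shift = 0.284/0.961 × 0.499 = 0.148 h, about 9 min.

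**Closed form, the plan's SD and correlation.** Later nights still share some of the run-in variation, so that covariance is subtracted. Take mean 7.0 h, no between-person variation, SD 2 h, AR(1) 0.95.
- f(14) = 0.799, so the variance of the run-in mean is 4 × 0.799 = 3.20 and its SD is 1.79.
- Average correlation of run-in with treatment nights = 0.95(1 − 0.95^14)(1 − 0.95^84)/(0.05² × 14 × 84) = 0.163, so the covariance is 0.65.
- Shift = (3.20 − 0.65)/1.79 × 0.798 = 1.14 h, about 68 min. Adding the 180-minute rule lowers it to 58 min in simulation.

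**Simulation, zero true effect, both rules applied.** Entries are for entrant means 6.0 / 6.5 / 7.0 h. The rate is the chance that at least one component in an arm shows a significant increase (two-sided 5%; 4–7% without selection), from a GEE with linear trend.

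| Scenario | Simple change, min | Rate, independence | Rate, AR(1) 0.95 |
|---|---|---|---|
| (a) SD 2 h, AR(1) 0.95, no between-person SD | 21 / 40 / 58 | 13 / 23 / 37% | 8 / 11 / 14% |
| (b) as (a), between-person SD 1 h | 17 / 32 / 48 | 10 / 17 / 28% | 7 / 9 / 12% |
| (c) SD 1.5 h, correlation 0.3, between-person SD 0.8 h | 3 / 8 / 14 | 10 / 26 / 53% | 6 / 7 / 10% |
| (d) SD 1 h, independent nights, between-person SD 1 h | 1 / 2 / 3 | 8 / 13 / 20% | 6 / 7 / 7% |

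More than one working correlation is needed because section 12 does not say what its unstructured matrix spans. Over 98 nights it would have 98 × 99/2 = 4,851 parameters; over seven period means, 7 × 8/2 = 28. The seven-period version gives rates close to independence (14 / 23 / 36% in (a), 13 / 29 / 51% in (c)).

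**What the trend removes.** The bias is a step or a decay after the run-in, not a straight line. With mean 6.5 h, between-person SD 0.75 h, nightly SD 1.25 h and correlation 0.3 (7 h cut only), 6.3 min becomes 6.2 min under independence and 6.0 min with a matching AR(1) matrix. At SD 2 h and AR(1) 0.95 (both rules), about 5 to 36 min remain under independence and about 1 to 6 min under AR(1) 0.95. AM/PM exposure has no bearing on selection.

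**Component contrasts at 6.5 h.** Off by about 10 to 12 min in (a) and under 1 min in (c).

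**Adherence rule alone.** Simple change −19 / −12 / −8 min in (a), −20 / −15 / −10 in (b), about −2 / −1 / 0 in (c) and under 0.3 min in size in (d). Adding the self-reported screen of section 7, modelled as a true 90-day mean under 7 h, gives −13.6 to +9.1 min across the settings tried.

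**The case against.** The strongest reply is that the size is overstated. Scenario (a) uses the plan's maximum SD and no between-person variation. The simple change is only to be reported, while the effect is to be assessed with the trend-adjusted GEE. Under an AR(1) 0.95 working matrix that GEE gives rates of 6 to 14%. With weakly correlated nights the shift is 1 to 14 min, small against an effect size of 0.7 (42 min if it means hours, 84 min if it means units of a 2 h SD). All of this stands as a limit on size. It does not remove the bias, and the plan does not commit to the working correlation that would shrink it most.

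A second reply is that sections 11 and 12 randomise on adherence alone. They omit the 7 h check but do not cancel it, and sections 3 and 9 require eligibility as well as adherence. With both rules applied the shift was upward in every scenario run.

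A reader might go further and infer that, if adherence alone governed, the shift would be downward. The documents do not support that. The 180-minute rule does little when nights are weakly correlated. It is framed as a wear check, so short nights may be device gaps. The self-reported under-7 h screen would still apply and can reverse the sign.

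**Conclusion.** The concern holds. If the run-in check under 7 h decides entry, as sections 7 and 16 say, the primary within-arm change is biased upward and nothing in the plan removes this. Confidence in the existence and direction of the bias is high. Its size is uncertain, because the entrant mean, the between-person SD and, below the plan's maximum, the nightly SD and correlation are all assumed. The range is about 1 to 14 min with weakly correlated nights and about 17 to 58 min at 2 h and AR(1) 0.95. The linear trend helps in the second case and hardly at all in the first, unless a correlation stronger than the data's is imposed.

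Under the adherence rule alone the 180-minute requirement pushes the shift down or leaves it near zero, and the net direction is undetermined once the self-report screen is counted. Even with the changes below, other changes over time are handled only by the linear trend, so attribution to the intervention stays limited.

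**What to change.** 1. Reconcile sections 7 and 16 with sections 11 and 12 on who is randomised, and state whether the 7 h check uses the run-in average. The reading matters: at an entrant mean of 6.5 h, requiring most, 80% or every night under 7 h gives 41 / 60 / 72 min in (a) and 9 / 21 / 29 min in (c). This costs wording only.

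2. Label the simple change from run-in as descriptive, state that it includes regression to the mean, and do not rest a conclusion of meaningful increase on it alone. This costs wording only.

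3. Add an analysis that uses the 2-week follow-up, already collected, as a second untreated period. At 6.5 h this cuts the shift from 40 to 15 min in (a) and from 8 to 4 min in (c); it does not remove it. It is conservative if benefit carries over into follow-up.

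4. As a sensitivity analysis, not a replacement for the primary analysis, fit a linear mixed model to nightly sleep. Use a person random intercept, AR(1) residual plus independent nightly error, linear time, arm-specific component effects and the AM/PM covariate. Include the run-in nights of consented people not randomised because they slept 7 h or more.
   - State that it relies on the covariance model, on roughly normal person means and on recorded sleep being true sleep. With strongly skewed person means, about 5 of 12 min remained in (c).
   - Show it with and without people removed for low recorded sleep. With 15% poor wearers assumed, including them left about 5 to 6 of 6.2 min in (c) at 6.5 h, and excluding them gave about −2 min.
   - Confirm that the consent covers these data. They are collected after consent, but section 16 addresses data use only for people who choose to withdraw.

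No new visits or participants are needed. The cost is analysis time and the consent check.

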## **4. OBJECTIVE(S)/SPECIFIC AIMS AND HYPOTHESES**

- *A concise statement of the goal(s) of the current study.*
- *The rationale for and specific objectives of the study.*
- *The goals and the hypothesis to be tested should be stated.*

The goal of the Roybal Center for Personalized Trials is to focus on innovative, behavioral interventions aimed at promoting and improving the overall health and well-being of older adults through the conduct of fully powered, meaningful, personalized trial pilots. The goal of this project is to evaluate the effects of a combined Mind-Body Intervention on increasing sleep duration in middle aged women working in health care, and to determine which intervention component proved most effective for each individual participant

Thus, the aims of this pilot study are :

**Primary Aim:** Determine if a personalized trial testing a Mind-Body Intervention (MBI) can produce a meaningful increase in the average daily sleep duration among women 40 – 60 years of age working in healthcare.

**Exploratory Aim 1:** Evaluate the effect of the MBI on sleep quality and other physiological factors.

**Exploratory Aim 2:** Explore the role of anxiety and depression as a potential mediator between perceived stress and sleep quality before, during, and after the MBI.

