### **Sample size justification:**

The primary aim of this study is to evaluate the effect of a personalized MBI on increasing the average daily sleep duration in working at Northwell Health. A sample size of 30 participants per arm achieve 80% power to detect a minimum effect size of 0.7 expected by one of the three Aim 2 interventions. Calculations were based on GEE tests for repeated measures considering a total of 28 daily measurements (4 weeks) per intervention, at a significance level of 0.05. The within subject standard deviation  $\sigma$  is anticipated to be maximum 2h, with an auto-regressive AR(1) base correlation of 0.95 taken at two successive timepoints. Estimated effect size and correlation values were derived from a previous fatigue study that employed similar intervention/design and collected sleep duration as exploratory endpoint.

The **randomization schedule** will be set up by a member of the Institute of Health System Science data team and provided to the data analyst assigned to this trial.. Randomization will occur with a fixed seed value for the purposes of repeatability and auditability, and the list of participants will be split into two groups using a

random shuffle function that takes that seed as input. The order in which an individual becomes eligible for one of these randomizations will determine the placement given (i.e. the first person eligible will be randomized to the intervention order given to participant 1 and continue sequentially). Eligibility is obtained by a participant maintaining at least 80% adherence of survey response, Fitbit wear  $\geq 12$  hours a day 80% of days, and 80% sleep data  $\geq 180$  minutes available through the baseline run-in period. The data analyst will alert the research coordinator of the assigned randomization once a participant becomes eligible during the baseline run-in period. As this pilot is not blinded to study coordinators, this concealed allocation involving the data analyst alerting the study coordinator of intervention assignment will be used to prevent bias by blinding the sequence up until time of randomization.

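### The goal is to find the best component and only component order is randomised, yet every contrast the plan names is against the run-in, so no difference between components is specified

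*Combined protocol and SAP*

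**What the plan says.** Section 4 sets two goals: to evaluate the combined intervention on sleep duration, and to "determine which intervention component proved most effective for each individual participant". Section 3 (Rationale for MBI Intervention Components) repeats the second goal. Section 8 fixes two mirror sequences, ABCCBA and CBAABC, with A mindfulness, B yoga and C guided walking, in 2-week blocks: "Eligible participants will be randomized (1:1) into Arm 1 or Arm 2". The 2-week run-in always comes first and carries no intervention.

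In section 12 (Analytical Plan) the primary outcome is "Mean Within-Subject Difference in daily sleep duration during 3 treatment periods from baseline". The summaries match it: "Individual changes in the average daily sleep durations between the run-in and each treatment period will be reported", as means with 95% CIs. The effect on an "individual's sleep duration will be assessed in each arm separately". The model sentence is "The effects of treatment on sleep duration will be assessed using generalized estimating equations (GEE"), followed by the covariance, linear trends and an AM/PM covariate, but no reference level and no contrast. The exploratory outcomes are also defined as changes from baseline. Exploratory Aim 2 adds a mediation model, which is not a treatment contrast.

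**The concern.** Which component is best is a question of one component against another. The only factor assigned at random is component order, so a component difference is the one quantity for which randomisation can give protection. The plan names no such difference. It also keeps the arms apart, and within one arm the order is the same for everyone, so an arm-by-arm analysis cannot draw on the randomisation at all.

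Someone who wants a ranking is left with three changes from run-in. Subtracting two of them gives a point difference, but not its interval: the changes share the same 14 run-in nights and are correlated, and the two separate intervals do not show by how much. The likely shortcut is to note which change excludes zero, and that is not a test of a difference. The run-in changes also absorb anything that shifts sleep between run-in and intervention and is not captured by the model.

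**Working it through.** **1. The plan's own power figure.** Section 12 gives 30 per arm, alpha 0.05, 28 nights per component, SD at most 2 h, AR(1) 0.95, and "80% power to detect a minimum effect size of 0.7 expected by one of the three Aim 2 interventions". Neither the unit of 0.7 nor the comparator is stated. The variance of a mean of 28 consecutive nights is 0.654σ². For two groups of 30, two-sided:

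- 0.7 in SD units: Φ(0.7/√(2×0.654/30) − 1.96) = Φ(3.35 − 1.96) = 91.8%.
- 0.7 h (0.35 SD): Φ(1.68 − 1.96) = 38.8%.

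A figure near 80% needs an unstated assumption, such as compound symmetry (79.4%) or component minus run-in at 0.7 h pooled over 60 (78.1%). The 80% therefore cannot be tied to any one contrast and is not used below.

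**2. Drift.** The blocks of the three components are 1 and 6, 2 and 5, 3 and 4. Each pair has mean position 3.5, which is 49 days (7 weeks) after the run-in mean. An assumed unmodelled linear drift of 0.05 h/week adds 7 × 0.05 = 0.35 h to every change from run-in. It adds 0 to every component difference.

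**3. What the randomisation protects.** Let p1 to p6 be period effects common to both arms.

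- Mindfulness minus walking picks up (p1+p6−p3−p4)/2 in Arm 1 and the exact negative in Arm 2. Averaged over arms, any period pattern cancels.
- Yoga is in blocks 2 and 5 in both arms. Yoga minus mindfulness, averaged over arms, keeps (p2+p5)/2 − (p1+p3+p4+p6)/4. This is zero for a linear trend, but not in general.

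**4. Ranking from run-in results when all three components are equal.** Assumptions: true effect 0.7 h for each, SD 2 h, AR(1) 0.95 throughout, 30 in one arm, two-sided 0.05, no missing data, no carryover. With independence weighting, the variance of component minus run-in, in units of σ², is component variance + run-in variance − 2 × covariance, and SE = 2√(variance/30).

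| Blocks | Variance | SE (h) | Power |
|---|---|---|---|
| 1, 6 | 0.4140 + 0.7991 − 2×0.2615 = 0.690 | 0.303 | 64% |
| 2, 5 | 0.4601 + 0.7991 − 2×0.1385 = 0.982 | 0.362 | 49% |
| 3, 4 | 0.6540 + 0.7991 − 2×0.0900 = 1.273 | 0.412 | 40% |

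The three test statistics have correlations of 0.67 to 0.85. Simulation from their joint normal distribution gives the chance that some components reach significance and others do not:

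| Case | Mixed verdicts |
|---|---|
| 0.7 h, SD 2 h, independence weighting | about 37% (33% with a linear time term) |
| 0.7 h, SD 2 h, AR(1) weighting (SEs 0.113, 0.138, 0.159 h) | about 0.7% (0.9% with a linear time term) |
| 0.7 h, SD 1 h, independence weighting | about 8% |
| 1.4 h (0.7 SD), SD 2 h, independence weighting | about 8% |
| 0.3 h, SD 2 h, AR(1) weighting | about 37% to 38% |

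The third and fourth rows agree because the ratio of effect to SE is the same.

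**5. The direct contrasts.** Both arms, 60 participants, independence weighting, SD 2 h, AR(1) 0.95:

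- Mindfulness minus walking has variance 0.699σ², so SE = 2√(0.699/60) = 0.216 h. The difference detectable with 80% power is 2.80 × 0.216 = 0.60 h.
- Yoga minus either of the others has SE 0.149 h, giving 2.80 × 0.149 = 0.42 h.
- For one participant, mindfulness minus walking has SE 2√0.699 = 1.67 h, a 95% half-width of about 3.3 h.

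**The case against.** The strongest reply is that the run-in comparison is the right one for the primary aim. Section 4 asks whether the intervention increases sleep duration, and section 3 states that goal relative to the baseline period. That stands: the gap is against the second goal, not the primary aim.

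Four stronger readings are tempting, and the documents do not support them.

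- **That the component comparison is ruled out.** The GEE sentence names no reference level, so a component contrast could be taken from the model. It is unspecified rather than excluded, and could be chosen after the data are seen.
- **That the plan will call one component effective and another not.** Section 12 reports means with intervals and states no rule for ranking by significance. Mixed verdicts are a risk in interpretation, not a planned procedure. Their frequency turns on the working correlation, and the unstructured matrix in section 12 leaves the actual weighting unclear. The 2 h SD is also the plan's stated maximum.
- **That randomisation protects every pairwise comparison.** It swaps only mindfulness and walking.
- **That the stated 80% power belongs to a run-in contrast.** Section 12 names no comparator.

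It can also be said that group contrasts do not tell one participant which component suits her. That is correct, and the remedy must include per-participant differences.

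Finally, section 12 says the model accounts for linear trends. If a time term is fitted, linear drift is removed from the run-in changes too, and the 0.35 h illustration applies only to drift that the model misses.

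**Conclusion.** The point holds in a limited form. The plan has a goal that needs component differences and a design that can supply them, but it names only changes from a fixed, non-randomised run-in, analysed arm by arm. As written, it makes no use of the randomisation and specifies no estimate or interval for a difference between components. This should be corrected, but it does not invalidate the primary aim.

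The size of the interpretation risk depends on assumptions. Mixed verdicts among equal components range from about 0.7% to about 37% at 0.7 h, depending on the weighting. They are about 8% at SD 1 h or at 1.4 h, and return to about 37% under AR(1) weighting at 0.3 h. The drift figure rests on an assumed 0.05 h/week. The structural gap depends on none of these numbers.

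**What to change.** In the Analytical Plan of section 12:

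1. Keep the changes from run-in for the primary aim, and label them as before-and-after estimates.
2. Add direct component contrasts for sleep duration from one model over both arms, using each component's two blocks, each with a 95% CI. Name mindfulness minus walking as the randomised contrast. Give yoga minus each of the others as resting on the linear-trend assumption.
3. Report the same component differences with CIs for each participant, since section 4 asks the question at that level.
4. State that any claim that one component is better than another rests on these contrasts only.

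The cost is a few sentences and a few contrast lines from the same data, with no extra participants or procedures. The downside is that some rankings may have to be reported as inconclusive, especially for single participants, given the half-width of about 3.3 h under the plan's maximum SD and independence weighting.
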